3. SUMMARY OF STUDY PLAN

Protocol chairperson: [name] FACS, University of Wisconsin

Primary Endpoint: The primary objective is to determine if there is a difference in EGFR phosphorylation in normal appearing bladder epithelium adjacent to tumor approximately 9-18 hours post-study dose, between patients randomized to erlotinib weekly as compared to placebo.

The prioritized secondary objectives are: 1) to assess the tolerance of high dose weekly erlotinib compared to placebo. 2) to assess the expression of phosphorylated EGFR in tumor tissue when available. 3) to assess the expression of e-cadherin and Ki67 in normal and abnormal urothelium. 4) to assess the expression of phosphorylated ERK in normal and abnormal urothelium. 5) to assess limited

pharmacokinetics of weekly erlotinib. 6) to assess the expression of p53 in normal and abnormal urothelium. 7) to assess the expression of let-7 in normal and abnormal urothelium. 8) perform an exploratory assessment of men on whether urination symptoms alter while on study.

Study Schema:

This is a multi-center, phase IIa randomized, double-blind, placebo-controlled study. Participants will be randomized on a 1:2 ratio to placebo vs. active study agent and stratified according to planned surgery (TURBT vs. cystectomy) and use of agents that significantly decrease Erlotinib bioavailability (tobacco, protein pump inhibitors). Fifteen participants will be enrolled on the placebo arm. A maximum of 30 participants will be enrolled on the active intervention arm. The accrual goals account for an anticipated dropout rate of 5-10%. Total anticipated accrual is therefore 45 participants.

There will be six sites participating in the study. Each randomized patient will be treated with study medication weekly x 3 doses. We will allow for study duration of approximately 3 years.

- Placebo or
- Erlotinib (with allowance for a 50% dose reduction for adverse events as specified in section 5.6)

Participants for this protocol will be accrued from a population of males and females 18 years of age and older who have a confirmed or suspected bladder tumor which will be treated with TURBT (or planned cystoscopy with biopsies) or cystectomy (total or partial). Eligible participants will be randomly assigned to either 600 mg erlotinib PO or matching placebo once weekly for 3 doses preceding their scheduled bladder surgery. The study will be terminated when all participants have completed study dosing, their scheduled surgical treatment, and a 7-14 day post-surgery follow-up period.

There is no run-in period specified for this protocol. Potential study participants will be identified from the population of patients being evaluated and treated for bladder tumors at each of the participating institutions. After being presented with information about the protocol, patients interested in participating will be scheduled for a screening/baseline study visit. After completion of the informed consent process, the following assessments/procedures will be conducted:

Screening/Baseline visit (within 30 days of first dose of study agent):

- eligibility assessment
- medical/surgical history and baseline symptoms
- physical exam/vital signs (including performance status assessment)
- clinical safety labs (including pregnancy testing for females of childbearing potential)
- plasma pharmacokinetics
- request for randomization
- International Prostate Symptom Score (I-PSS)

Study agent and topical ointment (topical clindamycin, topical hydrocortisone) dispensing: (within 30 days of baseline assessments) either in clinic or study agent will be mailed to the participant via overnight courier with a phone contact prior to dosing. Ointment instructions will be included (See Appendix B).

- study agent dosing instructions
- ointment instructions
- concomitant medication review and adverse event assessment

Pre Day 8 Phone contact (approximately 24-72 hours prior to Day 8 Visit):

- instruct participant on dose and time of Day 8 study drug administration

Day 8 Visit*:

- physical exam/vital signs (including complete assessment of any rash per CTCAE criteria)
- clinical safety labs
- plasma pharmacokinetics
- Day 8 Study dosing after plasma pharmacokinetics
- concomitant medication review, compliance and adverse event assessment

*The day 8 clinic visit will be optional; if the participant opts out then a post day 8 phone contact (within 48 hours of taking dose) will be required for a concomitant medication review, compliance and adverse event assessment.

Pre-Surgery reminder Phone contact (approximately 24-72 hours prior to Surgery):

- instruct participant on dose and time of pre-surgical study drug administration

Surgery visit: (Day 15-16):

- physical exam/vital signs
- clinical safety labs
- plasma pharmacokinetics
- concomitant medication review, compliance and adverse event assessment
- International Prostate Symptom Score (I-PSS)
- collection of paraffin-embedded blocks or slides after standard pathology processing

Post-Surgery phone contact (7-14 days post-surgery):

- concomitant medication review and adverse event assessment

Duration of study participation will range from 29-56 days depending upon how long before the day 1 study agent dosing occurs after the screening/baseline assessments.

4. PARTICIPANT SELECTION

4.1 Inclusion Criteria

4.1.1 Participants must have a confirmed or suspected invasive or non-invasive bladder tumor (initial or recurrent) discovered on cystoscopy or radiologic imaging performed within 120 days of randomization.

4.1.1.1 Patients with muscle invasive bladder cancer (MIBC) must have never received and currently be ineligible for cisplatin-based neoadjuvant chemotherapy due to any of the following:

- 1) calculated creatinine clearance of < 60 ml/min
- 2) KPS < 80
- 3) solitary kidney or
- 4) patient refusal to undergo neoadjuvant chemotherapy.

4.1.2 The participant may have prior treatment for bladder tumor (excluding radiation therapy) provided that treatment:

- Was completed greater than 30 days prior to the first dose of study agent

4.1.3 Participants must be a candidate for a trans-urethral resection of the bladder tumor (TURBT), cystectomy (partial or radical) or cystoscopy with biopsy at a participating organization.

4.1.4 Age ≥ 18 years. Because no dosing or adverse event data are currently available on the use of high dose weekly erlotinib in patients less than 18 years of age, children are excluded from this study but will be eligible for future pediatric trials, if applicable.

4.1.5 Karnofsky $\geq 60\%$; see Appendix A

4.1.6 Participants must have normal * organ and marrow function as defined below:

4.1.6.1 Hematologic:

WBC $\geq 3000/\text{mm}^3$;
platelets $\geq 100,000/\text{mm}^3$,
hemoglobin >10 g/dL

4.1.6.2 Hepatic:

alkaline phosphatase ≤ 1.5 X upper limit of normal
bilirubin ≤ 1.5 X upper limit of normal
AST ≤ 1.5 X upper limit of normal
ALT ≤ 1.5 X upper limit of normal
Bilirubin for Gilbert's ≤ 3.0 mg/dl

4.1.6.3 Renal:

A calculated Creatinine clearance (Cockcroft Gault) of ≥ 30 ml/min

4.1.6.4 Electrolytes:

Sodium ≥ 130 mg/dl and \leq upper limit of normal
Potassium ≥ 3.0 mg/dl and \leq upper limit of normal

*Normal limits are defined as the normal range appearing on the results report for the clinical laboratory providing the clinical laboratory testing.

4.1.7 The effects of erlotinib on the developing human fetus at the scheduled weekly dose are unknown. For this reason women of child-bearing potential and men must agree to use adequate contraception (hormonal or barrier method of birth control; abstinence) prior to study entry and for the duration of study participation. Should a woman become pregnant or suspect she is pregnant while participating in this study, she should inform her study physician immediately.

4.1.8 Ability to understand and the willingness to sign a written informed consent document.

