2.2 Study Agent

Erlotinib HCl (Tarceva) is an orally available, highly selective, reversible inhibitor of epidermal growth factor receptor (HER1/EGFR) tyrosine kinase. Inhibition of tyrosine kinase activity prevents HER1/EGFR phosphorylation, the associated downstream signaling events, and may block tumorigenesis mediated by inappropriate HER1/EGFR signaling. Erlotinib inhibits the intracellular phosphorylation of tyrosine kinase associated with the EGFR. The recommended dosing in adults is a daily oral dose of 150 mg continuously or until dose-limiting toxicity leads to an interruption and possible reduction in daily dosing.

Erlotinib pharmacokinetic analyses have been characterized by the following observations; a relatively long half-life (10-12 hours), predominant metabolism via P450 metabolism with some correlation to hepatic function, and increasing AUC values with repeated daily dosing (White-Koning 2011, Hamilton 2006). Also multiple studies have correlated an increasing AUC of erlotinib or gefitinib with the occurrence of skin toxicity (White-Koning 2011, Thomas 2009) while there are other studies, which have not confirmed this association (Calvo 2007). Current smokers have been observed to tolerate erlotinib and gefitinib better than non-smokers but also to have less benefit observed. Consistent with these observations Hamilton et al (Hamilton 2006) performed a comparison pharmacokinetic study of erlotinib in current smokers and non-smokers at doses of 150 and 300 mg. They observed that current smokers had AUC and Cmax values approximately half of non-smokers or smokers at 300 mg had AUC values similar to non-smokers at 150 mg daily. It is theorized the likely explanation of this is the known contribution of CYP1A1 and CYP1A2 to the metabolism of erlotinib and their induction by cigarette smoking.

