4.2 Exclusion Criteria

4.2.1 Any treatment for the bladder tumor other than intravesical therapy between the pre-study cystoscopy or radiologic imaging which identified the suspected bladder tumor and the scheduled surgical removal or cystoscopy-guided biopsy of that tumor.

4.2.2 Any chemotherapy and/or radiation therapy received ≤ 3 months of study entry and any immunotherapy received ≤ 6 months of study entry (with the exception of BCG treatment).

4.2.2.1 Any prior external beam radiation to the pelvis.

4.2.3 A concurrent skin rash or skin condition requiring treatment with a prescription medication.

4.2.4 The following medications may not be taken within 24 hours of the first dose of study agent or at any time while a participant is taking study agent due to the risk of significant drug-drug interaction.

- Coumadin
- Strong CYP3A4 inhibitors (which lead to decreased erlotinib metabolism/increased erlotinib levels) including ketoconazole, atazanavir, boceprevir, ceritinib, clarithromycin, cobicistat, darunavir, dasabuvir, idelalisib, indinavir, itraconazole, lopinavir, nefazodone, nelfinavir, ombitasvir, paritaprevir, posaconazole, ritonavir, saquinavir, telaprevir, telithromycin, troleandomycin, voriconazole, and grapefruit or grapefruit juice.
- CYP3A4 inducers (which lead to increased erlotinib metabolism/decreased erlotinib levels) including rifampicin, rifabutin, rifapentine, phenytoin, carbamazepine, phenobarbital, primidone, enzalutamide, fosphenytoin, lumacaftor, mitotane, and St. John's Wort.
- Agents which decrease gastric acid are allowed but should be avoided if possible.
- Participants may resume inhibitors or inducers of CYP3A4 > 14 days after their last dose of study agent

4.2.5 Participants requiring daily use of non-steroidal anti-inflammatory drugs (NSAIDs), with the exception of ≤ 81 mg aspirin per day. During study participation, acetaminophen is preferred for treatment of pain; the use of NSAIDs, as needed for pain, is discouraged.

4.2.6 Participants may not be receiving any other investigational agents.

4.2.7 History of allergic reactions attributed to compounds of similar chemical or biologic composition to erlotinib or clindamycin (topical agent for potential skin toxicity).

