4.3 Inclusion of Women and Minorities

Both men and women and members of all races and ethnic groups are eligible for this trial. Because of the demographics and incidence history at our consortium sites we expect a predominance of white males, which reflects the incidence of bladder cancer. The University of Wisconsin Chemoprevention consortium sites see an average of 76% male patients and 89% white patients. However, many of our consortium sites serve ethnically diverse areas. Urology San Antonio has shown successful recruitment with Hispanic and Latino patients (25% of diagnoses, 49.1% of the population), and Johns Hopkins University serves communities that are much more diverse with populations between 25-40% African-American. Johns Hopkins University and the Carolina Urologic Research Center of Myrtle Beach, SC both of which serve a more diverse patient population are recent additions to the Consortium. The Carolina Urologic Research Center has one of the largest bladder cancer populations in the country.

The UWCCC continues to look for innovative ways to increase the minority participation in our own clinical trials, despite the demographic profile of our community. This is the focus of several initiatives of the UWCCC Cancer Control Program. In addition to devising more effective means of reaching local minority populations, the UWCCC's affiliate minority recruitment has been strengthened through affiliated research networks, examples being the Wisconsin Oncology Network or the Wisconsin Network for Health Research (both started by the Consortium PI/[name]) which includes multiple clinical sites in Milwaukee county where underserved populations approach 20% compared to <10% in UWCCC's catchment area. Another underserved population that our affiliated research networks help with is the rural poor and the elderly poor. This is especially true with the Wisconsin Network for Health Research which has many clinic sites in rural defined areas with median incomes at or near the poverty line. In addition, the UWCCC has multiple ongoing initiatives to encourage underrepresented communities participation in health care research including efforts by Study PI/Chair, [name], who performs monthly outreach to local African-American churches for cancer and clinical research awareness.

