factors for severe hepatic dysfunction have included pre-existing liver dysfunction from cirrhosis, viral hepatitis, hepatocellular carcinoma, hepatic metastases, or concomitant treatment with potentially hepatotoxic drugs.

Erlotinib can cause fetal harm when administered to a pregnant woman; therefore, women should avoid becoming pregnant while being treated with erlotinib. Adequate contraceptive methods should be used during therapy and for at least two weeks after completing therapy. There are no adequate and well-controlled studies in pregnant women using erlotinib; however, studies in animals have shown some reproductive toxicity. Breastfeeding should be discontinued during erlotinib therapy. While it is not known whether erlotinib is excreted in human milk, in animals erlotinib and/or its metabolites were excreted in milk.

Please see Concomitant Medications Section.

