7.4 Evaluation at Completion of Study Intervention

At the end of study participation, the participant will have research blood work and evaluations for toxicity. The results of these analyses will be compared to the baseline results. At the end of study intervention the following procedures must be completed. The end of study visit has some critical timing requirements to allow for accurate pharmacokinetic measurements in the blood. The final dose of study drug should be taken on the day before surgery on an empty stomach. The participant should be instructed to take this final dose in the evening prior to the day of their surgery. The end-of-study pharmacokinetic blood work must happen approximately 9-18 hours after the last dose of study drug was taken. Please document the date and hour: minute of the last study dose along with the date and hour: minute of the pharmacokinetic blood draw.

Laboratory analyses for safety: **WBC, platelets, hemoglobin, Hct, BUN, total bilirubin, AST, ALT, alkaline phosphatase, creatinine, sodium, potassium, chloride and bicarbonate.**

The participant's **vital signs**, including weight, blood pressure, pulse rate, respiration rate and temperature will be taken.

A review of **concomitant medications** focusing on any changes to the medication list since study initiation and any new medications started since study initiation. Participants should be questioned about medications that have been discontinued prior to surgery.

The coordinator should collect and calculate study **drug compliance**.

International Prostate Symptom Score (I-PSS) – would be completed prior to surgery and the coordinator would collect this.

The participant and coordinator should review any **adverse events** that took place during study participation. The coordinator should record the relevant details about the adverse events as outlined in protocol section 11.

To insure consistency in pharmacokinetic evaluations, all participants should have their end-of-study pharmacokinetic blood work and biomarkers within approximately 9-18 hours after the final dose of study medication. See section 10.2.2 for instructions on drawing and processing the end-of-study pharmacokinetics and biomarkers. Record the date and time of the pharmacokinetic blood draw and the date and time of the last dose of study drug.

Interventions at Time of Surgery

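### For women of child-bearing potential, section 4.1.7 lets contraception lapse as early as about 8 days after the last dose, against the two-week minimum in section 6.2

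*Combined protocol and SAP*

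**What the plan says.** Section 4.1.7 requires women of child-bearing potential, and men, to agree to adequate contraception "prior to study entry and for the duration of study participation". The end point is therefore the end of participation, not a time since the last dose.

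Section 6.2, after warning of fetal harm, states: "Adequate contraceptive methods should be used during therapy and for at least two weeks after completing therapy".

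Four other provisions fix the dates:

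- Section 7.4 tells the participant to "take this final dose in the evening prior to the day of their surgery". Section 5.2 puts that dose about 9-18 hours before surgery.
- The last scheduled event in section 3 is the "Post-Surgery phone contact (7-14 days post-surgery") call.
- Section 8.4 allows a participant to go off study once the intervention and required follow-up are complete. It also allows earlier exits, for example for withdrawal, an adverse event or physician decision.
- Section 4.2.4 already uses an interval counted from the last dose for another purpose: CYP3A4 inhibitors and inducers may resume only more than "14 days after their last dose of study agent".

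**The concern.** The two sections set different end dates for the same precaution, and the criterion that participants sign up to is the shorter one. Because follow-up is anchored to surgery and may close after a week, a woman can comply fully with 4.1.7 and still stop before the period in 6.2 has passed.

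Nothing else in the available text closes the gap. Appendix B mentions harm to an unborn baby but gives no contraception instruction. The post-surgery call covers only concomitant medication and adverse events. The pregnancy test is scheduled only at baseline.

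What is at stake is avoiding fetal exposure, and six sites having one clear rule to apply. No endpoint or analysis is affected. The conflict concerns women only, because 6.2 sets no interval for men.

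**Working it through.** The two-week figure is a stated rule, so there is nothing to reproduce. The check is calendar arithmetic followed by a rough estimate of remaining drug.

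**Inputs.** Last dose on Day 15 and surgery on Day 16 (sections 5.2 and 7.3); final call d = 7 to 14 days after surgery (section 3); required interval 14 days (section 6.2); "a relatively long half-life (10-12 hours") from section 2.2; consortium sites that "see an average of 76% male patients" (section 4.3); 45 participants, 30 of them on erlotinib (section 13.3).

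**Days from last dose to final call.** Gap = (16 + d) − 15 = d + 1. Shortfall = max(0, 14 − gap).

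| Call, days after surgery | Days after last dose | Days short of 14 |
|---|---|---|
| 7 | 8 | 6 |
| 8 | 9 | 5 |
| 9 | 10 | 4 |
| 10 | 11 | 3 |
| 11 | 12 | 2 |
| 12 | 13 | 1 |
| 13 | 14 | 0 |
| 14 | 15 | 0 |

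Six of the eight permitted call days fall short. This counts days in the window. It is not a forecast of how often sites will call early, since no distribution of call dates is given.

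**By the clock.** With the dose 9-18 hours before surgery, a day-7 call comes 7 + 9/24 = 7.38 to 7 + 18/24 = 7.75 days after it.

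**Delayed surgery.** The last dose moves with the operation (section 5.2), so the earliest gap does not change. For surgery on Day 17, 22, 23 or 28, taking the last dose as the day before, the gap to a day-7 call is again 8 days.

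**Drug remaining at the earliest call.** Elapsed time is 7 × 24 + 9 = 177 h to 7 × 24 + 18 = 186 h. That is 177/12 = 14.75 to 186/10 = 18.6 half-lives. Under simple first-order decay the fraction left is 2^(−14.75) = 0.0036% down to 2^(−18.6) = 0.00025%.

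**Early exit.** A woman who leaves the study 24 h after a dose has no further duty under 4.1.7. By then 24/12 = 2 to 24/10 = 2.4 half-lives have passed, leaving 2^(−2) = 25% down to 2^(−2.4) = 19% of that dose. The reassuring figure above does not cover this case.

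**Number of women.** At 24% female, 0.24 × 45 = 10.8, about 11 women in all, and 0.24 × 30 = 7.2, about 7 on erlotinib. The number of child-bearing potential is lower and is not given.

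**The case against.** The strongest reply is that the difference has no practical consequence. Almost no drug remains at the earliest scheduled call, section 4.2.9 already requires a negative pregnancy test before dosing, and the number of women affected could be zero. That is largely right for women who complete follow-up, and it limits how serious the point is. It does not make the two sections agree, and it does not cover an early exit.

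A second reply is that 6.2 is general background on the agent and 4.1.7 is the trial rule, so a site can satisfy both by following the longer period. A careful site would. But 6.2 is the only place in the available text that gives a post-dose interval, and 4.1.7 itself says the fetal effects of the weekly dose are unknown, which is no basis for a shorter period.

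A third reply uses the 29-56 day duration of participation in section 3. With no lead time from screening, 29 days would reach Day 29-30, which is at least two weeks after the Day 15 dose. But the range is counted from screening. Screening 7 days before Day 1, surgery 15 days after Day 1 and a call 7 days later also gives 7 + 15 + 7 = 29. The range also does not match the visit windows: with surgery on Day 16 and a lead of 0 to 30 days, they give 0 + 15 + 7 = 22 to 30 + 15 + 14 = 59 elapsed days. It cannot be relied on to guarantee the two weeks.

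Finally, participants act on the consent form, which was not available and may already say two weeks. That stands as a limit on what can be said about practice. It does not settle the conflict between 4.1.7 and 6.2.

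**Conclusion.** The point holds. As written, 4.1.7 lets the contraception duty for women of child-bearing potential end as early as 8 calendar days after the last dose, up to 6 days before the minimum in 6.2. The shortfall applies to calls on post-surgery days 7-12 and disappears on days 13-14.

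This assumes that participation ends at the post-surgery call, as section 8.4 permits. It would end later for someone followed under section 13.7 for an unresolved drug-related event, and sooner for someone who leaves early. A woman who stops study drug before the last planned dose but stays in follow-up has a longer gap.

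The expected harm is small, and the trial's results are not affected. The case for changing the text is that an eligibility rule is less protective than the protocol's own stated period and can be corrected at almost no cost.

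**What to change.** Amend 4.1.7 so that women of child-bearing potential agree to adequate contraception from before study entry until at least two weeks after their last dose of study agent, whenever participation ends, including an early exit under section 8.4. For a Day 15 last dose this carries the duty to at least Day 29. The earliest scheduled end of participation is now Day 23, so the change adds at most 6 days for anyone who completes follow-up, and nothing when the call is 13-14 days after surgery. Check that the consent form gives the same period.

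The cost is one sentence in the protocol and a check of the consent wording. Visits, sample size and analysis stay as they are.
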